1 PROTOCOL SYNOPSIS

Title	A Multicenter Phase 2/3 Trial of the Efficacy and Safety of Intracerebroventricular Radioimmunotherapy using ^{131}I -omburtamab for Neuroblastoma Central Nervous System/Leptomeningeal Metastases
EudraCT number	2017-001828-22
Investigational New Drug (IND)	9351
Investigational site(s)	Several sites in Europe and US
Investigator	Trial Coordinating Investigator: [name]. Memorial Sloan-Kettering Cancer Center [name] USA
Sponsor	Y-mAbs Therapeutics [name] Denmark
Trial ID	101
Trial design	Single-arm, open-label Phase 2/3 trial
Patient population	Pediatric neuroblastoma (NB) patients with central nervous system (CNS) relapse as evidenced by CNS/leptomeningeal (LM) metastases
Objectives	Primary Objective 
1. To evaluate the overall survival (OS) rate at 3 years. Secondary objectives: 
1. To evaluate CNS/LM progression-free survival (CNS/LM PFS) at 6 and 12 months2. To evaluate Overall Survival (OS) at 12 months3. To evaluate the objective response rate (ORR) at 6 months.4. To evaluate dosimetry of ^{131}I-omburtamab.5. To evaluate the pharmacokinetics of ^{131}I-omburtamab.6. To evaluate safety of ^{131}I-omburtamab.7. To evaluate the immunogenicity of ^{131}I-omburtamab.
Endpoints	Primary Endpoint: 
1. OS rate at 3 years after the first treatment dose of ^{131}I-omburtamab. Secondary Endpoints 
1. CNS/LM PFS at 6 and 12 months2. OS at 12 months3. ORR assessed as a combination of partial response and complete response as defined by the Response assessment in Neuro-Oncology (RANO) group criteria for brain metastasis (Lin et al, 2015) or leptomeningeal metastases as defined by EANO-ESMO criteria (Le Rhun et al, 2017). ORR will be assessed at 6 months after the first treatment dose of ^{131}I-omburtamab4. ORR according to CSF cytology. Response is defined as a complete response when CSF converts from positive at baseline to negative after treatment with ^{131}I-omburtamab5. Whole-body, organ, blood, and CSF radiation dosimetry.6. Pharmacokinetic analysis of activity in blood and CSF including derivation of best-fit uptake and/or clearance parameters (half-times, maximum value) of time-activity concentration curves and of I^{131} residence times (i.e., cumulated activity) concentrations (in $\mu\text{Ci}\cdot\text{h}/\text{g}$).7. The frequency, type, and duration of treatment-emergent severe adverse events and serious adverse events, including clinically significant laboratory abnormalities. All

	
adverse events will be graded according to Common Terminology Criteria for Adverse Events (CTCAE), version 4.0.
 
8. Performance assessment to monitor gross changes in neurological function is performed at week 26 and subsequently every 6 months during trial period.
 
9. The rate of ADA occurrence assessed three weeks after the first and second treatment dose of ^{131}I-omburtamab

Patient selection criteria	
Inclusion criteria:
 
1. Patients must have a histologically confirmed diagnosis of NB with relapse in the CNS or LM.2. Patients need to have progressed in CNS/LM through induction therapy or have relapsed in CNS/LM following induction. CNS/LM progression/relapse is defined as LM disease or metastatic deposits in the CNS parenchyma, (excluding skull bone-based metastases).3. Stable systemic disease not requiring chemo/immunotherapy as judged by the investigator.4. Ventriculoperitoneal (VP) shunts (only shunts with programmable valves can be accepted) are allowed however should be closed (or adjusted to highest pressure setting) during Investigational Medicinal Product (IMP) infusion. It is recommended that the VP shunt remains closed for approximately 5 hours after treatment and then re-adjusted. The shunt readjustment times are at the discretion of the treating physician. Closure of VP shunt is done at the discretion of the treating physician and the VP shunt should at any time based on patient safety evaluation be re-opened at the assessment of the treating physician. Patients with ventriculo-atrial or ventriculo-pleural shunts are not eligible.5. Patients must be between birth and 18 years of age at the time of screening.6. Patients must have a life expectancy of at least 3 months as judged by the investigator7. Acceptable hematological status defined as:
• Hemoglobin ≥ 8 g/dL• White blood cell (WBC) count $\geq 1000/\mu\text{L}$• Absolute neutrophil count $\geq 500/\mu\text{L}$• Platelet count $\geq 50,000/\mu\text{L}$8. Acceptable liver function defined as:
• ALT and/or AST ≤ 5 times UNL• Bilirubin $\leq 3 \times$ UNL• In case either AST or ALT $\geq 3 \times$ UNL, bilirubin must be ≤ 2 UNL9. Acceptable kidney function defined as:
• Estimated glomerular filtration rate (eGFR) $>60 \text{ mL/min}/1.73 \text{ m}^2$ calculated by the 2009 revised Bedside Schwartz Equation (Appendix 3)10. Written informed consent from legal guardian(s) and/or child must be obtained in accordance with local regulations. Pediatric patients must provide assent as required by local regulations. 
Exclusion criteria:
 
1. Patients with primary NB in CNS.2. Patients must not have obstructive or symptomatic communicating hydrocephalus.3. Patients must not have worsening of neurologic function, according to the assessment by investigator, within 3 weeks prior to first dose of ^{131}I-omburtamab.4. Patients must not have an uncontrolled life-threatening infection.5. Patients must not have received cranial or spinal irradiation less than 3 weeks prior to first dose of ^{131}I-omburtamab in this trial.6. Patients must not have received systemic chemo/immunotherapy (corticosteroids not included) less than 3 weeks prior to enrollment in this trial.7. Patients must not have received any anti-B7-H3 treatment prior to enrollment in this trial.8. Patients must not have severe major non-hematologic organ toxicity; specifically, any renal, cardiac, hepatic, pulmonary, and gastrointestinal system toxicity must fall below


Grade 3 prior to enrollment in this trial. Patients with stable neurological deficits (due to brain tumor) are not excluded. Patients with Grade 3 or lower hearing loss are not excluded.
 
9. Patients must not be pregnant or breast-feeding.
 
10. Female patients of child-bearing potential (i.e. having experienced menarche) and male partners to female patients who do not agree to the use of effective contraception during treatment and for a period of 12 months after the last ^{131}I-omburtamab dose. Effective contraception for women is defined as intrauterine devices or hormonal contraceptives (contraceptive pills, implants, transdermal patches, hormonal vaginal devices, or injections with prolonged release). Effective contraception for male partners is defined as use of condoms. To be exempt from the requirement to use contraception after ^{131}I-omburtamab treatment, one of the criteria described in section 9.2.11 of this protocol must be met.
 
11. Fertile male patients who do not agree to the use of condoms during treatment and for a period of 12 months after the last ^{131}I-omburtamab dose. For a sterilized male patient to be exempt from the requirement to use contraception after ^{131}I-omburtamab treatment, he must have undergone surgical sterilization (vasectomy).
	
Methodology	This Phase 2/3 trial is a single-arm, open-label, non-randomized, multi-center efficacy, safety, and dosimetry trial of intracerebroventricular (intracerebroventricular meaning administration of a medicinal product into the cerebral ventricles (cerebral ventricular system) of the brain) ^{131}I -omburtamab in pediatric NB patients with CNS/LM metastases. Patients will receive up to two cycles of ^{131}I -omburtamab. In case the patient has a subsequent relapse in the CNS/LM after ^{131}I -omburtamab therapy during the follow-up period, re-treatment to target minimal residual disease can be considered and allowed. Safety and efficacy will be investigated with short-term follow-up at 26 weeks after treatment and with long-term follow-up for up to 3 years following treatment.
Number of patients (planned)	Trial 101 plans to enroll at least 32 patients
Trial outline	
Screening evaluations including medical history, physical and neurologic examination, hematology and clinical chemistry will be completed within 30 days of the first ^{131}I-omburtamab dose. MRI and CSF cytology will be completed within 3 weeks of the first ^{131}I-omburtamab dose and baseline performance testing is completed any time after diagnosis of CNS/LM metastases. ^{131}I-omburtamab is infused via an indwelling intracerebroventricular access device (e.g. Ommaya) and an Ommaya patency/CSR flow study is conducted prior to the first ^{131}I-omburtamab infusion. One ^{131}I-omburtamab cycle takes 4 weeks and includes a treatment dose, an observation period and post-treatment evaluations. An interim analysis, evaluating the dosimetry and pharmacokinetic endpoints as well as available safety and efficacy data, will be conducted on data from patients having received at least treatment cycle 1 (dosimetry and treatment dose) prior to January 1st, 2020. Starting January 1st, 2020, no further patients will be administered dosimetry doses.
 
Patients can be treated in an outpatient setting or may be admitted as inpatients for the treatment infusions.
 
Patients without Grade 4 toxicity, as described in section 6.1.4, and without objective disease progression (as determined by neurologic and/or radiographic examination) by MRI at week 4 in cycle 1 will be eligible to receive a second ^{131}I-omburtamab dosing cycle. Patients with Grade 3 toxicity will receive a second dosing cycle at the discretion of the investigator.
 
Patients who finish both treatment cycles and complete week-8 assessments will enter the short-term follow up phase. Patients who finish only one treatment cycle will be registered as early treatment discontinuation and continue to the short-term follow-up visit at week 26. If week-8 assessments are not or cannot be completed, the next visit will be the short-term follow up visit at week 26.
 
Patients will be monitored for adverse events during and after ^{131}I-omburtamab infusion. Patients will have pre- and post-treatment clinical assessments including neurologic examination, hematology and serum chemistry, blood and CSF cultures, endocrinology

	assessments, CSF analysis, and pre- and post ^{131}I -omburtamab performance testing. Performance testing will be performed at trial baseline, 3 months after the last ^{131}I -omburtamab infusion, and twice yearly thereafter at the discretion of the investigator.
IMP	Monoclonal antibody omburtamab is a murine immunoglobulin G1 (IgG1) antibody raised in BALB/c mice. Omburtamab recognizes tumor-associated antigen B7-H3. The purified antibody is stored in glass vials between -25 to -15°C. The patients will receive omburtamab antibody radiolabelled with radioactivity calibrated to 50 mCi per treatment cycle. There will be a treatment dose reduction for patients younger than 3 years of age.
Trial period and duration	Trial duration will be up to 3 years for each patient. Safety and efficacy assessments will be performed for 26 weeks after the first ^{131}I -omburtamab cycle, with long-term follow up for up to 3 years after start of treatment.
Statistical considerations	
An interim analysis to evaluate the dosimetry endpoint as well as available safety and efficacy data, will be performed on data from patients having received at least treatment cycle 1 (both dosimetry and treatment dose) prior to January 1st, 2020. Starting January 1st, 2020, no further patients will be administered dosimetry doses.
 
Final analysis will be performed when at least 32 treated patients have completed long-term follow-up (3 years or until death). OS rate at 3 years and its 95% confidence interval will be estimated using Kaplan-Meier methods. [REDACTED] PFS will also be analyzed using Kaplan-Meier methods. Dosimetry will be summarized with descriptive statistics (n, mean, median, standard deviation (SD), minimum, maximum).
 
Safety summaries will be provided for treatment exposure, patient disposition, adverse events, adverse events leading to discontinuation and serious adverse events, laboratory safety data (serum chemistry and hematology), vital signs, and physical examination. The incidence of adverse events will be tabulated and reviewed for potential significance and clinical importance.

2 LIST OF ABBREVIATIONS AND DEFINITION OF TERMS

ADR	Adverse Drug Reaction
AE	Adverse Event
ALT	Alanine aminotransferase
AST	Aspartate aminotransferase
BALB/c	BALB/c Mouse Sarcoma Virus
BUN	Blood Urea Nitrogen
CBC	Complete Blood Count
CGCCR	Central German Childhood Cancer Registry
CNS	Central Nervous System
CRA	Clinical Research Associate
CRF	Case Report Form
CRO	Contract Research Organization
CSF	Cerebrospinal fluid
CTCAE	Common Terminology Criteria for Adverse Events
DLT	Dose Limiting Toxicity
DMC	Data Monitoring Committee
DNA	Deoxyribonucleic Acid
DSRCT	Desmoplastic Small-Round-Cell Tumor
eCRF	Electronic Case Report Form
eGFR	Estimated Glomerular Filtration Rate
EAC	Event Adjudication Committee
EOT	End of Trial
FAS	Full Analysis Set
h	Hour
GCP	Good Clinical Practice
GMP	Good Manufacturing Practice
IgG	Immunoglobulin G
I.v.	Intravenous
IB	Investigator's Brochure
ICF	Informed consent form
ICH	International Conference on Harmonization
IEC	Independent Ethics Committee
IMP	Investigational medicinal product
IRB	Institutional Review Board
MBq	Megabecquerel
LDH	Lactate Dehydrogenase
LM	Leptomeningeal
MCH	Mean Cell Hemoglobin
MCHC	Mean Cell Hemoglobin Concentration
MCV	Mean Cell Volume
MedDRA	Medical Dictionary for Regulatory Activities
mCi	Millicurie
mg	Milligram
mGy	Milligray
mL	Milliliter
MRI	Magnetic Resonance Imaging
mSv	Millisievert
MSK	Memorial Sloan Kettering Cancer Center
MYCN	V-Myc Myelocytomatosis Viral Related Oncogene
NB	Neuroblastoma
NCI	National Cancer Institute
ORR	Objective response rate
OS	Overall Survival
PD	Progressive Disease
PET	Positron emission tomography

PI	Principal Investigator
PFS	Progression Free Survival
PK	Pharmacokinetic
PO	Per Os (by mouth)
PPS	Per Protocol Analysis Set
RANO	Revised Assessment in Neuro-Oncology
RBC	Red Blood Cells
ROI	Regions-of-interest
SAE	Serious Adverse Event
SAP	Statistical Analysis Plan
SAR	Serious Adverse Reaction
sc	Subcutaneous
SD	Standard deviation
SPECT	Single-Photon Emission Computed Tomography
SOC	System Organ Class
SOP	Standard Operating Procedure
SUSAR	Suspected Unexpected Serious Adverse Reaction
TEAE	Treatment-Emergent Adverse Event
TSH	Thyroid Stimulating Hormone
UNL	Upper Normal Limit
VP	Ventriculoperitoneal
WBC	White Blood Cells
WHO	World Health Organization

3 FLOW CHARTS

Table 1 Schedule of time and events

Dosing/Measurements/Evaluations	Trial Periods						
	Screening	1 ³¹ I-omburtamab Treatment Period ¹				Follow-up ²¹	Long Term Follow-up ²¹
	Day -29 to 0	Week 1 & 5	Week 2 & 6	Week 3 & 7	Week 4 & 8	Week 26	Weeks 52, 78, 104, 130 & 156
Informed consent	X ²						
Eligibility check	X						
Demographics, height, and body weight	X						
Medical, surgical and disease history	X						
Prior/concomitant medications	X	X	X	X	X	X ¹⁹	X ¹⁹
TSH/free and total T4 ³	X	X			X	X	X
Physical examination	X	X	X	X	X		
Vital signs ⁴	X	X	X	X	X		
Clinical chemistry & Hematology	X	X	X	X	X		
Performance test ⁶	X ⁵					X	X
MRI of the brain and spine ⁷	X ⁵				X	X ²²	
Neurotoxicity ⁸	X	X			X	X	
Placement of an indwelling intracerebroventricular access device (e.g. Ommaya) ⁹	X						
Ommaya patency/CSF flow study	X						
CSF for cytology, total protein, glucose, and cell count ¹⁰	X ⁵				X	X	
Blocking of thyroid ¹³¹ I uptake ¹¹	X ¹²	X	X		(X) ¹³		
Premedication (oral dexamethasone or an i.v. equivalent) ¹⁴		X					
Premedication with an anti-pyretic ¹⁵		X					
Conditional blood and CSF for culture ¹⁶		X ¹⁶					
Intracerebroventricular ¹³¹ I-omburtamab treatment dose ¹⁷		X					
Adverse events ¹⁸	X	X	X	X	X	X	X

Dosing/Measurements/Evaluations	Trial Periods						
	Screening	¹³¹ I-omburtamab Treatment Period ¹					Follow-up ²¹
		Day -29 to 0	Week 1 & 5	Week 2 & 6	Week 3 & 7	Week 4 & 8	
Pregnancy testing	X ²⁰					X ²⁰	X ²⁰
Clinical response assessment for CNS/LM metastasis ²³	X					X	X
Collection of information on systemic disease progression ²⁴		X	X	X	X	X	X
Collection of information on CNS/LM disease progression ²⁵							X
ADA blood and CSF ²⁶	X					X	
PK blood and CSF ²⁷		X	X				

¹ The ¹³¹I-omburtamab treatment periods is divided in 4-week cycles (if a patient will receive 1 or 2 cycles is at the discretion of the investigator). A cycle consists of a treatment dose in the first week, followed by observation, and samples are taken during week 2 and 3 where after post-treatment evaluations will take place during week 4. For more details about the ¹³¹I-omburtamab cycles see section 6.1.4.

² Informed Consent must be obtained before any trial related procedures. Procedures or tests that are performed as a part of standard clinical care prior to informed consent, and therefore, not for the purpose of the trial, do not need to be repeated at screening if they have been performed within the allowed screening timelines. In these cases, source documents must show that these procedures or tests were performed as standard clinical practice and not for the purpose of the present trial. In case the indwelling intracerebroventricular access device (e.g. Ommaya) is placed in connection with the tumor resection, the informed consent must be obtained prior to the surgery and can be done before the start of the screening period if necessary. The investigator is responsible for documenting this properly.

³ Thyroid stimulating hormone (TSH)/ free and total T4 to be assessed at screening, pre-dose week 1 and 4, pre-dose week 5 and 8, week 26 if applicable and weeks 52, 78, 104 130 and 156.

⁴ Measurements of pulse oximetry, heart rate, respiratory rate, temperature, and blood pressure.

⁵ To be performed within 3 weeks prior first IMP infusion.

⁶ Lansky Scale < 16 years, Karnofsky Scale \geq 16 years. Post week 26 every 6 months.

⁷ (Magnetic resonance imaging of the brain and spine to be completed before first IMP administration), at week 4 (\pm 4 days), 8 (\pm 4 days) and 26 (\pm 24-29 weeks)

⁸ Gross investigation of cranial nerves by physical examination and radiographical investigation as described in section 6.1.3. Evaluating neurological Adverse Events (AEs), the National Cancer Institute clinical neurotoxicity criteria will be used. Any patient that develops a Grade 4 neurotoxicity must be discontinued from treatment. The clinical neurotoxicity evaluation is to be conducted at screening and weeks 1, 4, 5, 8 and 26. The radiographic assessment of neurotoxicity and disease progression (by MRI) is to be conducted at screening, weeks 4 and 8 and week 26.

⁹ Only for patients who do not have an intracerebroventricular device already placed. The procedure must be conducted prior to first dose and after the patient has been assessed to be eligible to enter the trial.

¹⁰ If CSF sample is positive for abnormal cells or outside reference ranges for any of the following: 1. total protein 2. glucose 3. cell count, it must be repeated within 4 weeks of the sample at screening. If abnormal CSF glucose (CTCAE \geq Grade 2) is obtained, a fasting serum glucose is to be obtained at next patient visit. At week 26, the CSF analysis should include cytology only.

¹¹ Treatment with potassium iodide and Cytomel should be initiated 1 week prior to each ¹³¹I- omburtamab infusion in a cycle and continue until 2 weeks after ¹³¹I- omburtamab infusion in the same cycle..

¹² Thyroid protection should be initiated 1 week prior to IMP administration. See section 7.2.5 for further details.

¹³ Thyroid protection should be initiated 1 week prior to next IMP administration – this is only applicable for week 4 and not week 8. See section 7.2.5 for further details.

¹⁴ Beginning 24 hours before ¹³¹I-omburtamab administration please see section 6.1.2.

¹⁵ Given 1-2 hours prior to ¹³¹I-omburtamab administration, including oral acetaminophen/paracetamol and antihistamine (e.g., diphenhydramine), please see section 6.1.2¹⁶
Drawn and held for culture if elevated body temperature after dosing suggests infection rather than expected response to intracerebroventricular dosing.

¹⁷ Dose reduction: 50% (25 mCi) for patients < 1 of age and 33% (33.5 mCi) for patients age 1 year to < 3 years of age, respectively.

¹⁸ Non-SAE's captured from signing the informed consent form (ICF) to dosing should be recorded as medical history. AEs should be reported until 3 weeks after the last IMP administration. SAE's should be captured from signing the ICF. Starting at week 4 (for patients receiving only one cycle) and starting at week 8 (for patients receiving both cycles) only SAEs considered related to ¹³¹I-omburtamab or new onset of cancers regardless of causality should be reported.

¹⁹ Limit to therapy related to cancer.

²⁰ In case fertile women (experienced menarche prior to screening or during treatment, until week 8) are enrolled; pregnancy testing should take place at screening, at week 4 and week 8, and at follow-up at week 26.

²¹ Follow-up at week 26 (24-29 weeks after first treatment) and Long-term follow-up visits at Weeks 52, 78, 104, 130 & 156 (\pm 4 weeks) can be done at referral site.

²² If done at referral site imaging parameters as required in the Imaging Manual should be followed to the extent possible.

²³ If this is the screening visit record any significant findings on the medical history page. For other visits evaluate the clinical status according to the following comparison to the previous assessment: Improved, Stable or Worse. See section 9.2.10.

²⁴ If systemic disease progression has occurred, this information is to be collected in the eCRF

²⁵ If CNS/LM disease progression has occurred, this information is to be collected in the eCRF

²⁶ Blood and CSF sampling for ADA will be done at baseline, 3 weeks after the 1st treatment (wk 4) and 3 weeks after the 2nd treatment dose (wk 8). 2 mL of blood and 0.5 mL of CSF will be collected per timepoint and sampling will be conducted conservatively given the age of the patients

²⁷ Blood and CSF PK sample collection will be done 1h after treatment, 6h after treatment, 24h after treatment and 7 days after treatment (wk 2 & wk 6) for both cycles. 2 mL of blood and 0.5 mL of CSF will be collected per timepoint and sampling will be conducted conservatively given the age of the patients, See section 9.1.2.7

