6.1.2 Treatment

Patients can be treated in an outpatient setting or may be admitted as inpatients for the treatment infusions. Local safety instructions for storage and handling of radioactive drug products must be strictly followed. Radiation safety precautions may include patient isolation and the use of lead shielding, or designated rooms to ensure that the dose rate in the surrounding areas meets regulatory requirements.

Thyroid protection must be ensured by adequate stable iodide saturation by use of e.g. oral potassium iodide and Cytomel (liothyronine sodium or equivalent). Thyroid protection should be initiated 1 week prior to first ^{131}I -omburtamab infusion in a cycle and continue until 2 weeks after last ^{131}I -omburtamab infusion in the same cycle. Thyroid protection is administered in relation to each treatment cycle. Please refer to section 7.2.5 for details.

[REDACTED]

[REDACTED]

[REDACTED]

[REDACTED]

[REDACTED]

A treatment dose of ^{131}I -omburtamab is administered during week 1. The treatment dose is followed by a 3-week observation period followed by MRI, CSF cytology, and safety monitoring.

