7.1.1 Treatment

One ^{131}I -omburtamab cycle takes 4 weeks and includes a treatment dose followed by an observation period and post-treatment evaluations. The treatment dose is administered on day 1 of the first week in a cycle (according to **Table 1**). The patient will be followed for 4 weeks after the treatment dose. A full treatment is achieved when both cycles have been completed. Patients who finish both treatment cycles and complete week-8 assessments will enter the short-term follow up phase. Patients who finish only one treatment cycle will be registered as early treatment discontinuation and continue to the short-term follow-up visit at week 26. Please see Duration of treatment section 6.1.4.

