8.1.2 Secondary endpoints

1. CNS/LM PFS at 6 and 12 months will be estimated based on the time from first treatment dose to CNS/LM progression or death from any cause. Patients alive without CNS/LM progression at time of analysis, will be censored at last date of disease evaluation without evidence of progression.
2. OS at 12 months will be estimated based on the time from first treatment dose to death by any cause. Patients alive at time of analysis, will be censored at last date known to be alive.
3. ORR assessed as a combination of partial response and complete response as defined by the Response assessment in Neuro-Oncology (RANO) group criteria for brain metastasis (Lin et al, 2015) or leptomeningeal metastases as defined by EANO-ESMO criteria (Le Rhun et al, 2017). ORR will be assessed at 6 months after the first treatment dose of ^{131}I -omburtamab
4. ORR according to CSF cytology. Response is defined as a complete response when CSF converts from positive at baseline to negative after treatment with ^{131}I -omburtamab
5. Whole-body, organ, blood, and CSF radiation dosimetry.
6. Pharmacokinetic analysis of activity in blood and CSF including derivation of best-fit uptake and/or clearance parameters (half-times, maximum value) of time-activity concentration curves and of I-131 residence times (i.e., cumulated activity) concentrations (in $\mu\text{Ci}\cdot\text{h/g}$).
7. The frequency, type, and duration of treatment-emergent severe adverse events and serious adverse events, including clinically significant laboratory abnormalities. All adverse events will be graded according to Common Terminology Criteria for Adverse Events (CTCAE), version 4.0.
8. Performance assessment to monitor gross changes in neurological function is performed at week 26 and subsequently every 6 months during trial period.
9. The rate of ADA occurrence assessed three weeks after the first and second treatment dose of ^{131}I -omburtamab

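### Reporting of all adverse events closes 3 weeks after the last dose, at the start of the end-of-cycle visit week, so some severe events in the last week of the final cycle never reach secondary endpoint 7

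*Combined protocol and SAP*

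**What the plan says.** - **End of reporting.** Footnote 18 to Table 1: "AEs should be reported until 3 weeks after the last IMP administration". It continues: "Starting at week 4 (for patients receiving only one cycle) and starting at week 8 (for patients receiving both cycles) only SAEs considered related to" the study drug, or new cancers, are to be reported. Section 10.8 uses the same 3 weeks for SAEs regardless of cause. Section 10.9 uses it for follow-up of non-serious events.
- **Cycle and visit.** Section 7.1.1: "The treatment dose is administered on day 1 of the first week in a cycle", and "The patient will be followed for 4 weeks after the treatment dose". Footnote 1 to Table 1 describes sampling in weeks 2 and 3, "where after post-treatment evaluations will take place during week 4". Section 6.1.2 says that the dose is "followed by a 3-week observation period followed by MRI, CSF cytology, and safety monitoring". Table 1 schedules physical examination, chemistry, hematology, neurotoxicity, MRI and CSF at weeks 4 and 8.
- **What the data feed.** Item 7 of section 8.1.2: "The frequency, type, and duration of treatment-emergent severe adverse events and serious adverse events, including clinically significant laboratory abnormalities". Section 12.4 starts the treatment-emergent period at the first administration and gives it no end.

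**The concern.** The reporting window and the safety visit meant to close the cycle barely overlap. The plan observes each child for 4 weeks after a dose and puts safety monitoring after the third week, but for the final dose it stops collecting new adverse events as that monitoring begins.

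Endpoint 7 counts severe events as well as serious ones. A severe but non-serious event that starts in the final week is an adverse event by definition (section 10.1.1), yet it is not reportable. The comparison of safety events after dose 2 by antibody status (section 9.1.2.7.2) inherits the same cut-off.

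There is a link to trial oversight too. Section 19.1 halts enrolment for an unexpected sudden death during a treatment cycle and does not require relatedness. A cycle runs 4 weeks, but all-cause SAE reporting after the last dose runs 3.

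**Working it through.** **Inputs.** Dosing is on day 1 of the cycle (7.1.1). A cycle is 4 weeks (6.1.4, 7.1.1), so an undelayed second dose falls on day 29. Reporting closes 3 weeks after the last dose (footnote 18, 10.8). End-of-cycle evaluations take place in the fourth week of the cycle (footnote 1). Cycle 2 may be delayed by up to 8 weeks (6.1.4).

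**Formulas.** Closing day = dose day + 21. Study week = floor((day − 1)/7) + 1. Visit week = dose day + 21 to dose day + 27.

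| Last dose | Dose day | Reporting closes | Visit week | Visit-week days inside the window |
|---|---|---|---|---|
| Cycle 1 | 1 | day 22 (week 4) | days 22–28 | 1 of 7 if the closing day counts, 0 of 7 if not |
| Cycle 2, on schedule | 29 | day 50 (week 8) | days 50–56 | the same |
| Cycle 2, delayed 8 weeks | 29 + 56 = 85 | day 106 (week 16) | days 106–112 | the same |

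This reproduces the protocol's own mapping. Footnote 26 places antibody sampling "3 weeks after the 1st treatment (wk 4) and 3 weeks after the 2nd treatment dose (wk 8").

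**MRI window.** Footnote 7 allows ±4 days around weeks 4 and 8 but does not say which day anchors the window. In cycle 1:
- anchor day 22 (days 18–26): 5 of 9 days fall inside the reporting window;
- anchor day 25 (days 21–29): 2 of 9;
- anchor day 28 (days 24–32): 0 of 9.

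**What happens to an event on day 24 of the last cycle**
- Non-serious Grade 3 or 4 laboratory abnormality needing active management: an adverse event under 10.1.1, but not reportable under footnote 18.
- Grade 3 abnormality that becomes Grade 4 that day: a new adverse event under 10.6.4, and not reportable.
- SAE judged unrelated, other than a new cancer: outside 10.8.
- Related SAE, or related event of special interest (reported as an SAE under 10.8): reportable.
- Event that began on day 18 and is found on day 24: can be read as reportable, because 10.8 limits later SAEs by when they occur.
- Any of these on day 24 of cycle 1 in a child who then receives dose 2: reportable, because the 3 weeks run from the last dose.

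**Delay of cycle 2.** Read literally, the week 8 rule starts on day 50. With the maximum delay, that is 85 − 50 = 35 days before dose 2 and 106 − 50 = 56 days before the 3-week cut-off. The two sentences of footnote 18 then disagree.

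**After the change.** A limit at dose day + 27 (day 28 or 56) covers 7 of 7 visit-week days. By itself it covers 9, 8 or 5 of the 9 MRI days for the three anchors, which is why the limit must also reach the visit actually held.

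**The case against.** The best defence is that the gap is narrow and much of what matters is caught elsewhere. Most of that is fair:
- **Discovery at the visit.** A reader might infer that anything first found at the closing visit is lost. The text does not say so: 10.8 works by occurrence, so earlier onset keeps an event reportable.
- **Neurological events.** Neurotoxicity of Grade 3 or above is of special interest (10.4) and is reported as an SAE (10.8). Sections 6.1.3 and 9.2.10 allow new neurological signs to be presumed treatment related when progression is not clear. Such events are largely protected.
- **Myelosuppression.** It is tempting to cite 6.1.4 as expecting Grade 3 or 4 myelosuppression at week 4. It speaks of ongoing cases, which implies earlier onset, and blood counts are also scheduled in the first three weeks of each cycle.
- **Children who stop early.** A reader might infer a larger bias in this group. That is not shown: everyone has the same 3 weeks after the last dose, and 10.8 requires reports of events leading to discontinuation, with no time limit in that sentence.
- **Share of visits.** Spreading visits evenly over the week would put 6 of 7 after the cut-off. That spread is an assumption, it counts visits rather than events, and the synopsis accepts that week-8 assessments may not take place.
- **Laboratory values.** Section 12.4 summarises changes in laboratory parameters, so the values remain visible, though not as adverse events.
- **Sudden death.** Section 10.2 asks for it to be reported as an SAE, and deaths enter the survival endpoint. But 10.2 sets no period, whereas 10.8 does.

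The adverse-event mark in Table 1 at weeks 4 and 8 adds little, because the same row is marked at every later visit.

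What survives is the case by onset: severe, non-serious events not of special interest, and unrelated SAEs, that begin in the final week.

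**Conclusion.** The point stands in that limited form. On the nominal schedule the final 6 days of the last cycle (7 if the closing day is excluded) lie outside all-event and all-cause SAE reporting, although the plan schedules safety assessment in them. New severe, non-serious events not of special interest, chiefly laboratory abnormalities, and changes of grade counted as new events are left out of endpoint 7. Unrelated SAEs other than new cancers go unreported in days that section 19.1 still treats as part of a cycle.

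The direction is towards undercounting. The size cannot be computed, because the documents give no rate of events with onset in that week. The same days after dose 1 are covered in children who go on to cycle 2, so capture differs between cycles.

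The conclusion rests on dosing on day 1, on visits in the fourth week of the cycle, and on footnote 18 being applied as written.

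**What to change.** In footnote 18 and sections 10.8 and 10.9:
- End reporting of all adverse events and all-cause SAEs, and follow-up of non-serious events, at the later of (a) the end of the 4-week cycle after the last dose (28 days, counting the dosing day as day 1) and (b) completion of the end-of-cycle visit.
- If that visit is not held, use 28 days.
- Start the period limited to related SAEs and new cancers after that point.
- Define both periods from the last dose, not by week 4 or week 8, because cycle 2 can be delayed.

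The 28-day floor is needed. Section 6.9.3 brings discontinued children to the week 4 or 8 visit as soon as possible, so a rule tied to the visit alone could shorten their window. Section 12.4 should state the matching end of the treatment-emergent period.

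The cost is one amendment, about one more week of adverse-event entry per child, and a reported event rate that may rise slightly. No dose, visit or clinical rule changes.
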